#### 9.4.3. Other Analyses

Fat pads and injection procedure, quality of life outcomes and biomarker analyses, will be described in the SAP.

# 9.5. Interim Analyses

An interim analysis of all efficacy data will be performed when all randomized participants have completed the Day 60 visit or exited the study earlier. The purpose of this analysis is to identify early trends in the data for administrative planning of following studies. There is no plan to stop the study or drop a treatment arm based on the results from the interim analysis.

The final analysis will occur when all participants have completed the long-term safety follow-up or have exited the study earlier. The details of all analyses will be provided in the SAP which will be finalized before the interim analysis.

**10.** Supporting Documentation and Operational Considerations

# 10.1. Appendix 1: Regulatory, Ethical, and Study Oversight Considerations

# 10.1.1. Regulatory and Ethical Considerations

- This study will be conducted in accordance with the protocol and with the following:
  - Consensus ethical principles derived from international guidelines including the Declaration of Helsinki and Council for International Organizations of Medical Sciences (CIOMS) International Ethical Guidelines
  - Applicable ICH/ISO Good Clinical Practice (GCP) guidelines
  - Applicable laws and regulations
- The protocol, protocol amendments, ICF, investigator's brochure, and other relevant documents (eg, advertisements) must be submitted to an IRB/IEC and reviewed and approved by the IRB/IEC before the study is initiated.
- Any amendments to the protocol will require IRB/IEC approval before implementation of changes made to the study design, except for changes necessary to eliminate an immediate hazard to study participants.
- The investigator or designee will be responsible for the following:
  - Providing written summaries of the status of the study to the IRB/IEC annually or more frequently in accordance with the requirements, policies, and procedures established by the IRB/IEC
  - Notifying the IRB/IEC of SAEs or other significant safety findings as required by IRB/IEC procedures
  - Providing oversight of the overall conduct of the study at the site or at any home visits and adherence to requirements of applicable local regulations, for example 21 CFR, ICH guidelines, the IRB/IEC, and European regulation 536/2014 for clinical studies (if applicable)

# 10.1.2. Financial Disclosure

Investigators and sub-investigators will provide the sponsor with sufficient, accurate financial information as requested to allow the sponsor to submit complete and accurate financial certification or disclosure statements to the appropriate regulatory authorities. Investigators and sub-investigators are responsible for providing information on financial interests during the course of the study and for 1 year after completion of the study.

AGN-151607

### 10.1.3. Informed Consent Process

- The investigator or his/her representative will explain the nature of the study to the participant and answer all questions regarding the study.
- Participants must be informed that their participation is voluntary. Participants will be required to sign a statement of informed consent that meets the requirements of 21 CFR 50, local regulations, ICH guidelines, HIPAA requirements, where applicable, and the IRB/IEC or study site.
- The medical record must include a statement that written informed consent was obtained before the participant was enrolled in the study and the date the written consent was obtained. The authorized person obtaining the informed consent must also sign the ICF.
- Participants must be re-consented to the most current version of the ICF(s) during their participation in the study.
- A copy of the ICF(s) must be provided to the participant.

The ICF will contain a separate section that addresses the use of remaining mandatory samples for optional exploratory research. The investigator or authorized designee will explain to each participant the objectives of the exploratory research. Participants will be told that they are free to refuse to participate and may withdraw their consent at any time and for any reason during the storage period. A signature will be required to document a participant's agreement to allow any remaining specimens to be used for exploratory research.

### 10.1.4. Data Protection

- Participants will be assigned a unique identifier. Any participant records or datasets that are transferred to the sponsor will contain the identifier only; participant names or any information which would make the participant identifiable will not be transferred.
- The participant must be informed that his/her personal study-related data will be used by the sponsor in accordance with local data protection law. The level of disclosure must also be explained to the participant.
- The participant must be informed that his/her medical records may be examined by Clinical Quality Assurance auditors or other authorized personnel appointed by the sponsor, by appropriate IRB/IEC members, and by inspectors from regulatory authorities.

# 10.1.5. Committees Structure

An independent DSMB will review select safety data at scheduled times during the conduct of the study. Ad hoc meetings of the DSMB may be scheduled to evaluate potential safety signals, as needed. Policies, procedures, and composition of the DSMB are described separately in the DSMB charter for this study.

# 10.1.6. Posting Clinical Study Data

Study information and tabular study results will be posted to the US National Institutes of Health website www.clinicaltrials.gov.

#### AGN-151607

Study data and information may be published in nonpromotional, peer-reviewed publications either by or on behalf of Allergan.

Clinical study reports, safety updates and annual reports will be provided to regulatory authorities as required.

#### 10.1.7. Data Quality Assurance

- All participant data relating to the study will be recorded on eCRFs unless transmitted to the sponsor or designee electronically (eg, laboratory data). The investigator is responsible for verifying that data entries are accurate and correct by electronically signing the eCRF.
- The investigator must maintain accurate documentation (source data) that supports the information entered in the eCRF.
- The investigator must permit study-related monitoring, audits, IRB/IEC review, and regulatory agency inspections and provide direct access to source data documents.
- The sponsor or designee is responsible for the data management of this study including quality checking of the data.
- Study monitors will perform ongoing source data verification to confirm that data entered into the CRF by authorized site personnel are accurate, complete, and verifiable from source documents; that the safety and rights of participants are being protected; and that the study is being conducted in accordance with the currently approved protocol and any other study agreements, ICH GCP, and all applicable regulatory requirements.
- Records and documents, including signed ICFs, pertaining to the conduct of this study must be retained by the investigator in compliance with all applicable laws and regulations. No records may be destroyed during the retention period without the written approval of the sponsor. No records may be transferred to another location or party without written notification to the sponsor.

#### 10.1.8. Source Documents

- Source documents provide evidence for the existence of the participant and substantiate the integrity of the data collected. Source documents are filed at the investigator's site.
- Data entered in the eCRF that are transcribed from source documents must be consistent with the source documents or the discrepancies must be explained. The investigator may need to request previous medical records or transfer records, depending on the study. Also, current medical records must be available.
- Source data are defined as: original documents, data, and records (eg, hospital records, clinical and office charts, diaries or evaluation checklists, pharmacy dispensing records, recorded data from automated instruments, copies or transcriptions certified after verification as being accurate and complete, microfiche, photographic negatives, microfilm or magnetic media, X-rays, participant files, and records kept at the pharmacy, at the laboratories, and at medico-technical departments involved in the clinical study). These records include, but are

CONFIDENTIAL

not limited to, original signed and dated consent forms, relevant observations including records of AEs, and records of all exposure to study intervention.

### 10.1.9. Study and Site Closure

The sponsor designee reserves the right to close the study site or terminate the study at any time for any reason at the sole discretion of the sponsor. Study sites will be closed upon study completion. A study site is considered closed when all required documents and study supplies have been collected and a study-site closure visit has been performed.

The investigator may initiate study-site closure at any time, provided there is reasonable cause and sufficient notice is given in advance of the intended termination.

Reasons for the early closure of a study site by the sponsor or investigator may include but are not limited to:

- Failure of the investigator to comply with the protocol, the requirements of the IRB/IEC or local health authorities, the sponsor's procedures, or GCP guidelines
- Inadequate recruitment of participants by the investigator
- Discontinuation of further study intervention development

### **10.1.10. Publication Policy**

- Allergan as the sponsor has proprietary interest in this study. Authorship and manuscript composition will reflect joint cooperation between multiple investigators and sites and Allergan personnel. Authorship will be established prior to the writing of the manuscript. As this study involves multiple centers, no individual publications will be allowed prior to completion of the final report of the multi-center study except as agreed with Allergan. Allergan is solely responsible for determining what and when to publish.
- The sponsor will comply with the requirements for publication of study results. In accordance with standard editorial and ethical practice, the sponsor will generally support publication of multi-center studies only in their entirety and not as individual site data.
- Authorship will be determined by mutual agreement and in line with International Committee of Medical Journal Editors authorship requirements.

#### 10.1.11. Compliance with Protocol

The investigator is responsible for compliance with the protocol at the investigational site. A representative of the sponsor will make frequent contact with the investigator and his/her research staff and will conduct regular monitoring visits at the site to review participant and study intervention accountability records for compliance with the protocol. Protocol deviations will be discussed with the investigator upon identification. Protocol deviations will be reported to the IRB/IEC according to the IRB/IEC's reporting requirements.

# **10.2.** Appendix 2: Clinical Laboratory Tests

- The tests detailed in Table 10–1 will be performed by the central laboratory.
- Local laboratory results are only required in the event that the central laboratory results are not available in time for either study intervention administration and/or response evaluation. If a local sample is required, it is important that the sample for central analysis is obtained at the same time. Additionally, if the local laboratory results are used to make either a study intervention decision or response evaluation, the results must be entered into the eCRF.
- Protocol-specific requirements for inclusion or exclusion of participants are detailed in Section 5 of the protocol.
- Additional tests may be performed at any time during the study as determined necessary by the investigator or required by local regulations.

Laboratory Assessments	Parameters				
Hematology	Platelet countRBC indices:RBC countMCVHemoglobinMCHHematocritMCHCCoagulation (prothrombin time (PT), activated partial thromboplastin time (aPTT), and thrombin time (TT))% Reticulocyte		es	WBC count with differential (absolute): Neutrophils Lymphocytes Monocytes Eosinophils Basophils	
Clinical Chemistry	BUN Creatinine Glucose (nonfasting) Hemoglobin A1c	Potass Sodiu Calciu eGFR Chlori Albun	sium m im ide nin	AST ALT Alkaline phosphatase	Total direct and indirect bilirubin Total protein Lipid profile (cholesterol, triglycerides, HDL cholesterol, LDL cholesterol [calculated])
Routine Urinalysis	
 
Specific gravity
 
pH, glucose, protein, blood, ketones bilirubin, urobilinogen, nitrite, leukocyte esterase by dipstick
 
Microscopic examination (if blood or protein is abnormal)a
 
				
Other Screening Tests	• Urine human chorionic gonadotropin (hCG) pregnancy test) as needed-for women of childbearing potential a				

 Table 10–1
 Protocol-Required Safety Laboratory Assessments

ALT = alanine aminotransferase; AST = aspartate aminotransferase; BUN = blood urea nitrogen; eGFR = estimated glomerular filtration rate; HDL = high density lipoprotein; LDL = low density lipoprotein; MCV = mean corpuscular volume; MCH = mean corpuscular hemoglobin, MCHC = mean corpuscular hemoglobin concentration, RBC = red blood cell, WBC = white blood cell a Local urine testing will be standard for the protocol unless serum testing is required by local regulation or IRB/IEC.

a Local urine testing will be standard for the protocol unless serum testing is required by local regulation or IRB/I.

Investigators must document their review of each laboratory safety report.

#### AGN-151607

# 10.3. Appendix 3: Adverse Events: Definitions and Procedures for Recording, Evaluating, Follow-up, and Reporting

#### **Definition of AE**

AE	AE Definition		
•	An AE is any untoward medical occurrence in a patient or clinical study participant		

- An AE is any untoward medical occurrence in a patient or clinical study participant, temporally associated with the use of study intervention, whether or not considered related to the study intervention.
- An AE can therefore be any unfavorable and unintended sign (including an abnormal laboratory finding), symptom, or disease (new or exacerbated) temporally associated with the use of study intervention.

#### AE of Special Interest (AESI)

An AESI (serious or nonserious) is one of scientific and medical concern specific to the sponsor's study drug/device or program, which warrants ongoing monitoring and rapid communication by the investigator to the sponsor. Such an event might warrant further investigation in order to characterize and understand it.

The following AESI(s) have been identified for the study intervention in this protocol: possible distant spread of toxin (PDSOT).

Serious AESIs should be reported to the sponsor within 24 hours using the same reporting procedures for SAE reporting. Nonserious AESIs should be reported using the same procedures as nonserious AEs reporting by capturing the AE information in the source document and entering them into the eCRF. The Serious Adverse Event/Adverse Event of Special Interest Form for Interventional Studies should not be used to report any nonserious AESIs.

#### Events Meeting the AE Definition

- Any abnormal laboratory test results (hematology, clinical chemistry, or urinalysis) or other safety assessments (eg, ECGs, radiological scans, vital signs measurements), including those that worsen from baseline, considered clinically significant in the medical and scientific judgment of the investigator (ie, not related to progression of underlying disease); for example:
  - The test result is associated with accompanying symptoms, and/or
  - The test result requires additional diagnostic testing or medical/surgical intervention, and/or
  - The test result is considered to be an AE by the investigator or sponsor.
- Exacerbation of a chronic or intermittent pre-existing condition including either an increase in frequency and/or intensity of the condition

#### AGN-151607

- New condition detected or diagnosed after study intervention administration even though it may have been present before the start of the study
- Signs, symptoms, or the clinical sequelae of a suspected drug-drug interaction
- Signs, symptoms, or the clinical sequelae of a suspected overdose of either study intervention or a concomitant medication. Overdose per se will not be reported as an AE or SAE. Such overdoses should be reported regardless of sequelae.
- Lack of efficacy or failure of expected pharmacological action per se will not be reported as an AE or SAE. Such instances will be captured in the efficacy assessments. However, the signs, symptoms, and/or clinical sequelae resulting from lack of efficacy will be reported as AEs or SAEs if they fulfil the definition of an AE or SAE.

#### Events NOT Meeting the AE Definition

- Any clinically significant abnormal laboratory findings or other abnormal safety assessments that are associated with the underlying disease, unless judged by the investigator to be more severe than expected for the participant's condition. Merely repeating an abnormal test, in the absence of any of the above conditions, does not constitute an AE. Any abnormal test result that is determined to be an error does not require recording as an AE.
- The disease/disorder being studied or expected progression, signs, or symptoms (clearly defined) of the disease/disorder being studied, unless more severe than expected for the participant's condition
- Medical or surgical procedure (eg, endoscopy, appendectomy): the condition that leads to the procedure is the AE
- Situations in which an untoward medical occurrence did not occur (social and/or convenience admission to a hospital)
- Anticipated day-to-day fluctuations of pre-existing disease(s) or condition(s) present or detected at the start of the study that do not worsen

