## 2. Introduction

Allergan has developed a botulinum toxin type A neurotoxin complex, AGN-151607, for the prevention of post-operative atrial fibrillation (POAF) in patients undergoing cardiac surgery. AGN-151607 will be injected intraoperatively into discrete targets of the heart, namely the epicardial fat pads near the pulmonary veins and atria. The administration of AGN-151607 is intended to neuromodulate the ganglionic plexi in these regions, thus lowering the risk of developing POAF.

Atrial fibrillation (AF) is a supraventricular tachyarrhythmia with uncoordinated atrial activation and, consequently, ineffective atrial contraction (January 2014). Characteristics on an electrocardiogram (ECG) include:

- 1) Irregular R-R intervals
- 2) Absence of distinct P waves
- 3) Irregular atrial activity

AF is a common complication of cardiac surgery, occurring post-operatively in 30% to 60% of patients undergoing coronary artery bypass and/or cardiac valve surgical procedures, with an unchanged incidence over past decades (Mostafa 2012).

POAF is associated with recurrent AF, longer hospital stays (including in intensive-care settings), increased healthcare costs (in-hospital and post-discharge), higher risk of stroke, and increased mortality (Arsenault 2013; Kertai 2014; LaPar 2014; Mathew 2004); all of which reflect an increased clinical burden due to POAF, including the need for medical/procedural interventions.

Cardiac surgery via median sternotomy (open-chest or "open-heart" surgery) yields access to the epicardial fat pads, ie, the cardiac autonomic ganglionic plexi, which contain a rich network of nerves. These autonomic nerves have been targeted in several, customarily used ablative procedures to attenuate AF, both post-operative and more broadly. Surgical and catheter-based interventions (eg, ablations, surgical excisions of tissue) of the autonomic nervous tissue near the left atrial ostia of the pulmonary veins, including the epicardial fat pads, have demonstrated positive results in the prevention of recurrent AF (Katritsis 2011; Katritsis 2013; Pokushalov 2013; Gillinov 2016).

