# 9.2. Sample Size Determination

A sample size of 100 randomized participants per intervention group will provide approximately 80% power to detect the treatment difference between each of the AGN-151607 doses (assumed equally effective) and placebo for the primary efficacy endpoint. The power calculations are based on the following assumptions:

- The expected incidence of early postoperative AF within 30 days post-surgery will be 47.8% in the placebo group and 27.8% in each of the AGN-151607 groups. This assumption is based on the results observed in the Pokushalov study (Pokushalov 2015) and the Duke University Medical Center clinical trial discussed in Section 2 (Waldron 2019).
- Two-sided Mantel-Haenszel test statistic and a significance level of 0.05 for the test.

Calculations will be performed using commercial software PASS 2008 (Hintze 2008).

Assuming that approximately 10% in each intervention group will drop out early from the study, a total of approximately 330 participants will be randomly assigned to study intervention, in order to have approximately 300 participants complete all the efficacy assessments up to Day 60 visit.

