#### c. Requires inpatient hospitalization or prolongation of existing hospitalization

In general, hospitalization signifies that the participant has been detained (usually involving at least an overnight stay) at the hospital or emergency ward for observation and/or intervention that would not have been appropriate in the physician's office or outpatient setting. Complications that occur during hospitalization are AEs. If a complication prolongs hospitalization or fulfills any other serious criteria, the event is serious. When in doubt as to whether hospitalization occurred or was necessary, the AE should be considered serious.

Hospitalization for elective intervention of a pre-existing condition that did not worsen from baseline is not considered an AE.

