#### AGN-151607

## Recording and Follow-Up of AEs and/or SAEs

AE and	SAE Recording	
--------	---------------	--

- When an AE or SAE occurs, it is the responsibility of the investigator to review all documentation (eg, hospital progress notes, laboratory reports, and diagnostics reports) related to the event.
- An SAE should be reported to the sponsor via the paper forms provided within 24 hours.
- All AE or SAE information will then be recorded in the eCRF.
- It is **not** acceptable for the investigator to send photocopies of the participant's medical records to the sponsor in lieu of completion of the SAE CRF page.
- There may be instances when copies of medical records for certain cases are requested by the sponsor. In this case, all participant identifiers, with the exception of the participant number, will be redacted on the copies of the medical records before submission to the sponsor.
- The investigator will attempt to establish a diagnosis of the event based on signs, symptoms, and/or other clinical information. Whenever possible, the diagnosis (not the individual signs/symptoms) will be documented as the AE/SAE.

Assessment of Intensity		
MILD	A type of adverse event that is usually transient and may require only minimal treatment or therapeutic intervention. The event does not generally interfere with usual activities of daily living.	
MODERATE	A type of adverse event that is usually alleviated with additional specific therapeutic intervention. The event interferes with usual activities of daily living, causing discomfort but poses no significant or permanent risk of harm to the research participant.	
SEVERE	A type of adverse event that interrupts usual activities of daily living, or significantly affects clinical status, or may require intensive therapeutic intervention.	
An event is defin described in the	ned as serious when it meets at least one of the predefined outcomes as definition of an SAE, NOT when it is rated as severe.	

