11.1 Adverse Events

Adverse events will be coded by system organ class and preferred term using the Medical Dictionary for Regulatory Activities (MedDRA).

An AE will be considered a treatment-emergent adverse event (TEAE) if the AE began or worsened (increased in severity or became serious) on or after the date/time of the study injection. Per case report form instructions, a new AE record will be created with a new AE onset date/time for any AE that worsens. Therefore, TEAEs can simply be identified as those AEs with recorded onset date/time on or after the date/time of the study injection.

The number and percentage of participants reporting TEAEs in each study treatment group will be tabulated by descending percentage of the total across treatment groups, by system organ class and preferred term, and further categorized by severity and relationship to the study treatment. If more than 1 TEAE is coded to the same preferred term for the same participant, the participant will be counted only once for that preferred term. For tables presented by severity, the greatest severity observed will be used.

The number and percentage of participants who have treatment-emergent serious adverse events (TESAE) will be summarized by system organ class, preferred term and treatment group. A similar summary will be presented for subjects with TEAEs leading to discontinuation from the study. In addition, separate subject listings will be generated for deaths, serious adverse events (SAEs), and TEAEs leading to study discontinuation.

Cardiovascular events of interest in this study are: heart failure or congestive heart failure, stroke or transient ischemic attack, myocardial infarction, renal failure, respiratory failure, ventricular arrhythmias, and supraventricular arrhythmias. The number and percentage of participants who have treatment-emergent cardiovascular event of interest will be presented by treatment group. The list of preferred terms within each of the cardiovascular events of interest is provided below:

Heart failure or Congestive heart fa	nure	
Cardiac failure	Acute right ventricular failure	Acute pulmonary oedema
Cardiac failure acute	Chronic left ventricular failure	Pulmonary oedema
Cardiac failure chronic	Chronic right ventricular failure	Cor pulmonale
Cardiac failure congestive	Left ventricular failure	Cor pulmonale acute
Cardiac failure high output	Right ventricular failure	Cor pulmonale chronic

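### Appendix 3 gives conflicting directions on whether POAF is an AE or SAE, and the SAP plans no totals without AF/flutter, so TEAE and SAE totals partly reflect efficacy to an extent set by site reading

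*Protocol*

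**What the plan says.** POAF is the trial indication (Protocol Appendix 6). An episode of 30 seconds or more within 30 days of surgery is the primary endpoint (Protocol 9.4.1.1). On whether it is an adverse event, Protocol Appendix 3 (Section 10.3) points both ways.

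Away from reporting:
- Events NOT Meeting the AE Definition lists: "The disease/disorder being studied or expected progression, signs, or symptoms (clearly defined) of the disease/disorder being studied, unless more severe than expected". Neither document defines the expected signs, symptoms or severity of POAF.
- Events Meeting the AE Definition leaves lack of efficacy, taken alone, to the efficacy assessments.

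Towards reporting:
- The same list makes a condition first detected after dosing an AE. Inclusion criterion 6.01 requires sinus rhythm for 48 hours before randomization, so POAF will usually be new, although prior paroxysmal AF is allowed.
- It also says: "the signs, symptoms, and/or clinical sequelae resulting from lack of efficacy will be reported as AEs or SAEs if they fulfil the definition". This carries no condition about severity beyond expectation.
- A clinically significant ECG finding that needs intervention is an AE, with a carve-out for progression of underlying disease.
- SAE criterion c reads: "Complications that occur during hospitalization are AEs. If a complication prolongs hospitalization or fulfills any other serious criteria, the event is serious". Protocol Section 2 says: "AF is a common complication of cardiac surgery, occurring post-operatively in 30% to 60% of patients".

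Two further provisions link these. An SAE must first meet the AE criteria (Definition of SAE). The recording instruction is: "Whenever possible, the diagnosis (not the individual signs/symptoms) will be documented as the AE/SAE".

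SAP 11.1 states: "The number and percentage of participants who have treatment-emergent cardiovascular event of interest will be presented by treatment group". Supraventricular arrhythmias are one of those categories, and Table 11–1 names atrial fibrillation and atrial flutter as terms. TEAEs and treatment-emergent SAEs are tabulated by organ class and preferred term. The SAP text describes no version without AF and flutter.

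**The concern.** With approximately 20 to 40 sites (Protocol 4.1), two sites can follow the appendix in good faith and treat the same POAF case differently. One applies the disorder-under-study exclusion and reports nothing. Another applies the new-condition, sequelae or hospital-complication text and reports an AE or SAE.

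Investigators are blinded, so this variation does not by itself favour an arm. The difficulty is that POAF is the event the treatment is meant to reduce. Whatever share of POAF enters the AE database brings part of the efficacy difference with it, and site interpretation sets that share. The overall TEAE and SAE totals, the cardiac organ-class row and the supraventricular-arrhythmia row then mix safety with efficacy in unplanned proportions. A modest excess of other serious events on active treatment could look smaller in the totals than it is. There is also a compliance side: SAEs must reach the sponsor within 24 hours (Protocol 8.3.1), so a site needs to know whether stay-prolonging POAF is one.

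**Working it through.** **1. The text applied to four situations**

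| Situation | Text that leaves it out | Text that brings it in |
|---|---|---|
| POAF on the patch only, untreated | Disorder under study; lack of efficacy alone | New condition after dosing |
| Symptomatic POAF | Expected symptoms of the disorder; recording the diagnosis in place of the symptom leads back to the exclusion | Signs and symptoms of lack of efficacy |
| POAF treated by drug or procedure | Disorder under study | ECG finding needing intervention; for procedures, the bullet naming the underlying condition as the AE |
| POAF prolonging the index stay | Not an AE, so it cannot be an SAE | Hospital complication that prolongs the stay; sequela of lack of efficacy |

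The appendix states no order of precedence. The first row is the least contested, because two bullets agree on it. The conflict is sharper in the other three.

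**2. The plan's own figure**

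Inputs from Protocol 9.2 and SAP 13.0 are 47.8% against 27.8% and 100 per arm: "Two-sided Mantel-Haenszel test statistic and a significance level of 0.05 for the test"; "A sample size of 100 randomized participants per intervention group will provide approximately 80% power". The two-proportion normal approximation gives 83.6% power without continuity correction and 79.6% with it. Fisher's exact test gives 79.7%. The stated power reproduces, so the 20-point difference is the plan's working assumption.

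**3. How many participants are involved**

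With 330/3 = 110 per arm:
- Placebo: 110 × 0.478 = 52.6.
- Each active arm: 110 × 0.278 = 30.6.

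These are upper bounds, since they count every episode of 30 seconds or more. If 25% to 50% of POAF met a seriousness criterion (assumed), the SAE participants in question would be 13.1 to 26.3 on placebo and 7.6 to 15.3 in each active arm.

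**4. Effect on a total**

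Let p be the POAF rate, f the share of POAF reported as an event, and q the rate of non-AF events. Assuming independence, P(any event) = 1 − (1 − q)(1 − f·p). The documents give neither f nor q.

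Take q = 20% on placebo and 25% on active, a true excess of 5 points:
- f = 0.25: placebo 1 − 0.80 × 0.8805 = 29.6%; active 1 − 0.75 × 0.9305 = 30.2%; difference +0.7 points.
- f = 0.50: placebo 1 − 0.80 × 0.761 = 39.1%; active 1 − 0.75 × 0.861 = 35.4%; difference −3.7 points.

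Other assumed rates, active minus placebo in points:

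| Non-AF rates (placebo, active) | f = 0 | f = 0.25 | f = 0.50 | f = 1 |
|---|---|---|---|---|
| 20%, 30% | +10.0 | +5.3 | +0.6 | −8.8 |
| 80%, 90% | +10.0 | +8.3 | +6.6 | +3.2 |

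At a placebo non-AF rate of 20%, the excess that would be exactly cancelled is 4.3 points at f = 0.25, 9.3 at f = 0.50 and 22.2 at f = 1. The distortion is largest for SAE-type rates. An any-TEAE total that is already high is diluted, not reversed.

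**The case against.** The strongest reply is that the appendix can be read as a hierarchy. Both lists agree that POAF in itself is not an AE. The lack-of-efficacy sentence applies only to events that meet the AE or SAE definition, and an SAE must first be an AE, so the hospital-complication text cannot turn an excluded event into an SAE. The Introduction's description of AF as a complication is background, the diagnosis instruction only names events that already qualify, and the SAP term list tabulates whatever was reported. This reading is coherent, but the appendix does not state it. It also leaves the new-condition bullet unanswered and depends on an expected severity that is defined nowhere.

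Other parts of the reply stand, and they rule out stronger conclusions that a reader might infer:
- **That nobody could tell what the totals contain.** SAP 11.1 tabulates by preferred term and lists SAEs by subject, so reported AF can be counted and compared with patch-detected AF.
- **That a drug-induced rise in AF would go unseen.** It would appear in the primary endpoint, and AF burden, AF interventions and arrhythmia rehospitalization are also compared by arm.
- **That the totals are the main safety result.** The documents do not rank them so. The named event of special interest is possible distant spread of toxin, which has its own 40-term table.
- **That the DSMB does not see POAF by arm.** Its charter and separate SAP are not among these documents.

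The 5-point example is also below what the trial can detect. At 110 per arm, the standard error for 20% against 25% is √(0.16/110 + 0.1875/110) = 5.6 points and power is about 14%, so totals without AF would not reliably show that excess either.

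**Conclusion.** The conflict is in the text and should be resolved. POAF that is newly diagnosed, symptomatic, treated or stay-prolonging can be reported or omitted under different parts of the same appendix, and the SAP provides no totals that separate it out.

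The consequence is bounded. It reaches the overall TEAE and SAE totals, the cardiac organ-class row and the supraventricular-arrhythmia row. Other preferred-term rows and the toxin-spread table keep any excess of their own. Within the affected rows, the plan's 20-point POAF difference could dilute or offset a modest excess of other SAEs. How far depends on assumed non-AF rates, an assumed share of POAF reported, and independence. The reversal in the 5-point example needs a share near one half. These figures show direction and scale and do not predict this trial's results. It would go too far to say that the plan conceals a safety signal, because the data to separate AF from other events are collected and tabulated.

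**What to change.** **Protocol Appendix 3.** Reconcile the disorder-under-study exclusion, the new-condition and lack-of-efficacy bullets, the requirement that an SAE first be an AE, SAE criterion c and the diagnosis-recording instruction into one stated rule for POAF. It should cover POAF that is found on monitoring only, symptomatic, treated, stay-prolonging or a cause of readmission. More than one rule is acceptable and the choice is the sponsor's; what matters is that every site applies the same one.

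**SAP 11.1.** Present overall TEAE and SAE totals both with and without the atrial fibrillation and atrial flutter preferred terms, specified before the interim/primary unblinding described in SAP 12.0. The version without these terms is useful even if past reporting was uneven, since it depends little on how sites read the POAF rule. Symptoms or sequelae coded under other terms would remain in it.

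**DSMB.** Confirm from the charter and its separate SAP whether POAF by arm is already supplied.

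**Cost.** One extra version of the overview tables, a wording change and a site memo, with no new assessments. SAE reporting may increase, depending on the rule. If all serious POAF were made reportable, sites now reported none, and 25% to 50% of POAF were serious, the addition would be about 28 (13.1 + 2 × 7.6) to 57 (26.3 + 2 × 15.3) participants across the three arms, each under 24-hour reporting. A rule that leaves POAF out would add none.
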